A significant challenge of standard linear network models has been the discontinuity between one functional module and the next. The precision of cascade-driven network modeling will allow us to understand suprapostural dexterity without switching between different control modes. Cascade modeling allows us to articulate how seemingly differentiated forms can arise from similar fluid interactions across many timescales (Kelty-Stephen et al., 2022, 2013; Kelty-Stephen and Mangalam, 2022b). This capacity for cascades to extend across timescales appears similarly in postural sway, no matter whether we load the upper body (Furmanek et al., 2020; Kelty-Stephen et al., 2020), destabilize contact with the ground surface (Kelty-Stephen, 2018; Mangalam and Kelty-Stephen, 2021), or increase visual effort (Mangalam et al., 2021). Indeed, network modeling of cascade-like interactivity may reflect control parameters governing bodily coordination across the timescales of the fastest reflex to the slowest movement unfolding across the entire task. This modeling framework offers a new way to understand suprapostural dexterity in light of recent theoretical developments in cascade modeling and network physiology.

We will use network modeling of cascade-like interactivity as a fresh way to understand suprapostural dexterity in light of recent theoretical developments in cascade modeling and network physiology. The precision of cascade-driven network modeling will allow us to understand suprapostural dexterity without implying any discontinuity between one functional module and the next. Healthy adults will maintain an upright stance on a stable surface in one condition and perform the Trail Making Test while maintaining an upright stance in the other. We hypothesize that maintaining an upright stance would produce a functional network of multiplicative interactions among movement-system components (Hypothesis 1.1). The Trail Making Task has been shown to measure several capabilities

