such as cognitive flexibility, alternating attention, sequencing, visual search, and motor speed, among other functions (Bowie and Harvey, 2006; Reitan, 1958; Sanchez-Cubillo et al., 2009). Performing the Train Making Task must introduce longer-timescale constraints on the postural system already satisfying the shorter-timescale demands of postural stability. It is expected that the culmination of shorter-timescale postural constraints and longer-timescale constraints imposed by the Trail Making Task will produce more differentiated network configurations or modular networks. Accordingly, we hypothesize that taking part in the Trail Making Test would produce a succession of distinct, modular networks of multiplicative interactions among movement-system components (Hypothesis 1.2).

Aim 1 approach network modeling from the vantage point of traditional modeling that these modular networks should be static. In Aim 2, we will relax this premise to investigate how the cascade-like interactivity exhibits a continuum of variability within so-called modular networks and could underwrite the transitions between separate network configurations. Specifically, we will investigate how shorter-timescale perturbations destabilizing the upright stance interact with the longer-timescale constraints on task completion to facilitate transitions among different network configurations. We base our predictions on recent findings of functional brain networks, which suggest that performing two tasks simultaneously or in close succession relies on the flexible reconfiguration of the brain networks (Alavash et al., 2015; Ekman et al., 2012; Hilgetag et al., 2001; Lam and Shin, 1998). Indeed, performance in different concurrent tasks benefits from unique functional brain networks at various timescales: integration of local, intermediate, or global networks (Alavash et al., 2015). Furthermore, the inability of the brain networks to sustain two separate topological configurations at once, each supporting the performance in one of the dual-task components, causes moment-to-moment fluctuations in the dual-task behavior (Alavash et al., 2016). Accordingly, we will examine the extent of modularity and the strength of connectivity between modular networks on multiplicative interactions as part of Aim 2.

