Multifractality refers to blending processes across different timescales, producing emergent structures. Multifractal spectrum width will be estimated using Chhabra and Jensens (1989) direct method. A non-zero width will indicate interactions in component processes producing rapidly changing periods of variability, such as small and large changes in fluctuations. To identify whether a nonzero width reflects multifractality due to nonlinearity, the multifractal spectral width for the original series will be compared to those for 32 Iterated Amplitude Adjusted Fourier Transform (IAAFT) surrogates (Ihlen, 2012; Schreiber and Schmitz, 1996). IAAFT randomizes original values time-symmetrically around the autoregressive structure, generating surrogates that randomize phase ordering of the original series spectral

amplitudes while preserving linear temporal correlations. The one-sample t-statistic takes the subtractive difference between the multifractal spectrum widths for the original series and 32 surrogates, dividing by the standard error of the spectrum width for the 32 surrogates. The greater the value of the t-statistic, the greater the multifractality in the original series due to nonlinear as opposed to linear sources.

Network modeling of multiplicative interactions

Vector autoregression (VAR) analysis will be used to model multiplicative interactions across the CoP, CoM, and 79 markers, represented in the model as (CoP, CoM, M1, M2, ..., M79). VAR captures interdependencies amongst concurrent series and will model the effects of t-statistic across anatomical locations in subsequent segments. VAR will yield a temporal trajectory of weights for each combination, defining a directional weighted musculoskeletal network for each participant and task condition. These functional networks will be transformed into binary networks to compare with the anatomical network.

Thresholding the weights using a single, unique threshold value corresponding to the percolation threshold (Esfahlani and Sayama, 2018) will yield a minimally connected network across task conditions. In this sparse network, each node will be connected to at least one node by an edge at one of the layers of the multiplex network.

Statistical analysis

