A full-factorial regression model will test the impulses and responses of each marker position. Impulse and Response will serve as class variables indicating the locations of impulse and response variables. Statistical significance will be interpreted as evidence of the flow of nonlinearities in movement fluctuations between the corresponding pair of anatomical locations, with the flow direction from the Impulse variable to the Response variable. Statistical significance will be set at a Type I error rate of 5%.

Extraction of functional musculoskeletal modules

The Louvain algorithm will extract functional musculoskeletal modules from the entire network. Consensus clustering will be implemented to achieve a stable partition (Lancichinetti and Fortunato, 2012). Multiplex modularity analysis will identify the functional musculoskeletal modules across different task conditions---MolTi software (<https://github.com/gilles-didier/MolTi>) will be utilized to identify functional musculoskeletal modules within multiplex networks by optimizing multiplex modularity through the modified Louvain algorithm.

Comparison of functional musculoskeletal networks across task conditions

The networks will be coarse-grained to compare functional musculoskeletal networks across task conditions (Kujala et al., 2016). The functional modules estimated across task conditions will coarse-grain the binary networks and then compare the strength of the inter-

and intra-module connections across task conditions. The nodes in clustered networks represent modules, and the edges signify the relationships between modules.

D. Does this study involve the collection of blood, urine, saliva or other human biological material (HBM)?

No

DRUGS, BIOLOGIC DRUGS AND DEVICES

13. Drugs and Biologic Drugs

1. Does this research involve the use of drugs or biologics?

No

14. Devices

1. Does this research involve a medical device(s) (including an in vitro device [IVD] (assay), and medical software)?

No

CONFIDENTIALITY AND PRIVACY

15. Confidentiality and Privacy

A. Describe where research data will be stored. Check all that apply.

[contact] (secure UNMC or UNO designated cloud-based storage site)

◆ Microsoft Office 365 application (including SharePoint, OneDrive for Business, Teams or Streams) (UNMC, UNO or NU system instance) (secure UNMC or UNO designated cloud-based storage site)

Other secure UNMC or UNO designated cloud-based storage site - describe:

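### Aim 1's network and modules have no no-interaction reference: the percolation threshold and Louvain steps return multi-module networks from pure noise

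*Protocol*

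**What the plan says.** The two Aim 1 hypotheses stand in the protocol's Background and Rationale (Section II, item 3). The first is that "maintaining an upright stance would produce a functional network of multiplicative interactions among movement-system components (Hypothesis 1.1"). The second is that the Trail Making Test "would produce a succession of distinct, modular networks of multiplicative interactions among movement-system components (Hypothesis 1.2"). Neither comes with a null or a criterion for failure.

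The analysis is in 12.C. Under the network modeling heading, a VAR will "model multiplicative interactions across the CoP, CoM, and 79 markers", which gives directed weights for each participant and condition. The weights are then made binary: "Thresholding the weights using a single, unique threshold value corresponding to the percolation threshold" "will yield a minimally connected network across task conditions", so that "each node will be connected to at least one node by an edge at one of the layers". Under the module extraction heading, "The Louvain algorithm will extract functional musculoskeletal modules from the entire network". Consensus clustering is then used to stabilise the partition, and a multiplex version of modularity is optimised across conditions.

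Three other elements of 12.C bear on the point:
- 32 IAAFT surrogates are used to form a t-statistic for the multifractal spectrum width of each series.
- A regression with Impulse and Response as class variables is tested at 5%.
- Connection strength within and between modules is compared across conditions.

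**The concern.** Aim 1 asks whether locations on the body are coupled and whether that coupling is modular. The threshold is not a significance cut. It is tuned to the data so that a connected network results. Louvain then searches for the partition with the highest modularity, and a sparse graph will usually have one with clearly positive modularity even if its edges fell at random. Consensus clustering makes the partition repeatable but does not test it against anything.

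The IAAFT surrogates do not fill the gap. They ask whether each series on its own shows nonlinearity, and their result is the input to the VAR. They do not show what the VAR, threshold and Louvain steps return when locations are uncoupled.

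At stake is what a positive Aim 1 result would mean. If the same steps give a modular network from uncoupled data, reporting one does not tell coupling from its absence, and a modularity value in any condition has no chance level to be read against.

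**Working it through.** The protocol gives no figure on this point, so there is none to reproduce. The check has four steps.

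**Inputs**
- Nodes: CoP + CoM + 79 markers = 81 (12.C). Directed pairs: 81 × 80 = 6,480. Undirected pairs: 6,480 / 2 = 3,240.
- Conditions: four (12.A), taken as the layers. This is an assumption, because 12.C does not define the layers.
- Type I error rate: 5% (12.C).
- Noise weights: independent absolute standard normal values, made symmetric by taking the larger of the two directions. This is an assumption.

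**Step 1. The threshold is relative.** Let w(i,j,l) be the weight between locations i and j in layer l. If every location must have an edge in at least one layer, the highest threshold that allows this is

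t = min over i of [ max over j ≠ i and l of w(i,j,l) ],

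and an edge is kept if w ≥ t. Multiply all weights by any c > 0: t becomes c·t and the same edges are kept. The binary network is therefore the same whether the weights are large or close to zero.

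**Step 2. Noise through threshold and Louvain.** Modularity is Q = (1/2m) Σ [A(i,j) − k(i)k(j)/2m], summed over pairs in the same module, where A is the binary network, k the number of edges at a node and m the total number of edges. Results for the stance layer, 60 runs per row, counting modules of two or more nodes:

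| Layers sharing the threshold | Mean edges | Mean isolated nodes (range) | Modules, mean (min) | Q, mean (min) |
|---|---|---|---|---|
| 4 | 50.1 | 24.1 (8–43) | 12.3 (7) | 0.80 (0.65) |
| 2 | 101.1 | 7.2 (1–20) | 9.3 (6) | 0.61 (0.46) |
| 1 | 193.2 | 0 | 7.4 (5) | 0.42 (0.29) |

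Every run gave several modules. Requiring instead that the union of the layers be connected changed almost nothing (four layers: 12.3 modules, Q 0.79). Consensus clustering, added in 10 of the four-layer runs, gave 12.2 modules (minimum 8) and Q 0.80. The multiplex form of modularity was not simulated.

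Hand check of the isolated nodes with four layers: mean edges per node = 2 × 50.1 / 81 = 1.24; the share with none is about exp(−1.24) = 0.29; 81 × 0.29 = 23.5, close to the simulated 24.1.

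**Step 3. Stance weights smaller than the rest.** Four layers, with the stance weights multiplied by a factor and all weights still noise (40 runs per factor; the first row is from step 2):

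| Factor | Mean stance edges | Mean isolated nodes of 81 |
|---|---|---|
| 1.0 | 50.1 | 24.1 |
| 0.9 | 24.6 | 44.4 |
| 0.8 | 7.4 | 67.5 |
| 0.7 | 1.8 (none in some runs) | 77.4 |
| 0.5 | 0 | 81 |

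Coupling is absent in every row. Only the size of the stance weights relative to the other conditions changes, and that decides whether stance shows a network.

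**Step 4. The separate edge test.** Expected false positives over all directed pairs: 6,480 × 0.05 = 324. For markers only: 79 × 78 = 6,162 pairs, and 6,162 × 0.05 = 308. If the tests were independent, the chance of at least one over 6,480 pairs would be 1 − 0.95^6480, which is 1 to any practical precision.

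**The case against.** A reader might infer that Hypothesis 1.1 cannot fail, because the threshold leaves no location unconnected. The text does not support that. The guarantee is an edge in one of the layers, not in each, and stance on the stable surface is a single condition. Steps 2 and 3 show isolated nodes in the stance layer and, when its weights are half the others', no edges at all. This objection stands against the stronger reading. It does not rescue the rule, since stance then comes out empty because of relative weight size and not because a test found no interaction.

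A reader might also infer that Aim 1 as a whole carries no evidence. That goes too far as well. No sentence in 12.C says that a hypothesis is accepted once a thresholded network or a partition exists. One purpose given for the binary networks is to set them beside the anatomical network. 12.C also has a stated test of interaction, the 5% Impulse-Response test. That stands too, but the test is not tied to either hypothesis or to the thresholded network. With no stated adjustment, some significant pairs are close to certain without any coupling.

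Third, the rest of Hypothesis 1.2 (succession, distinctness, more differentiation than stance) is comparative, and Aim 2 is framed against stable standing, which goes through the same steps. Those contrasts have their own reference and are not part of this point.

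Last, 12.C is meant to be a short description, and a statistical analysis plan that is not shown may define a null. That is possible. But the protocol itself fixes the threshold rule, its intended outcome and the module algorithm, and the concern is with what those fixed rules produce. The comparison with the anatomical network is not a no-interaction reference.

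**Conclusion.** The point holds in limited form. Under the rules fixed in 12.C, the existence of a functional network (Hypothesis 1.1) or of modules (the modular part of Hypothesis 1.2) is not by itself evidence of coupling between locations. With noise layers of equal scale, every run gave a multi-module network: Q about 0.80 and about 12 modules in the stance layer with four layers, and Q about 0.42 and about 7 modules with one. With a shared threshold, whether stance shows a network depends on how large its weights are relative to the other conditions.

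The relative nature of the threshold (step 1) does not depend on how the weights are distributed. The values of Q and the module counts do. They rest on independent, symmetrised weights and on conditions as layers, whereas the planned VAR weights are directed and are likely to be correlated, so the real chance level will differ and has to be computed from the study's own data.

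**What to change.** Add a null reference for Aim 1 to 12.C, before results are seen:

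- Destroy the coupling between locations by permuting or circularly shifting each location's segment-wise t-statistic series independently of the others. A circular shift largely keeps each location's own serial dependence.
- Pass these series through the identical VAR, threshold, Louvain and consensus steps.
- Call Hypothesis 1.1 supported only if the observed VAR weights or connectivity before thresholding exceed the null. The comparison has to come before thresholding, because the threshold imposes the same connection rule on null data.
- Call the modular part of Hypothesis 1.2 supported only if modularity exceeds its null.
- Report modularity relative to the null in each condition. In noise, Q moved from 0.42 to 0.80 merely because a layer became sparser, so a single reference value for all conditions would not do.

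The cost is computing time and a few sentences in 12.C. No further participants or measurements are needed. The price is that Aim 1 could come out negative.

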
SECTION III

SUBMISSION DEADLINE

A. Full Board Review:

The IRB meets twice monthly, on the first and third Thursday of the month, with the exception of January and July when the IRB meets only on the third Thursday of the month. No more than 15 applications (e.g., initial review of a new study, re-review of a tabled study) will be reviewed at each meeting. All reviews are performed on a first-come first-served basis. The IRB meeting schedule and deadline dates can be found on the IRB website at www.unmc.edu/irb.

B. Expedited Review

Applications that qualify for expedited review have no submission deadline and can be reviewed independent of the IRB meeting schedule. Call the Office of Regulatory Affairs for assistance in determining if your study meets the requirements for expedited review.

ADDITIONAL REVIEW REQUIREMENTS

Final IRB approval and release of studies is contingent upon approval by the following UNMC committees or departments. Check the appropriate boxes:

UNMC and NM - Pharmacy & Therapeutics (P&T) Committee (Required for studies involving drugs)

Fred & Pamela Buffett Cancer Center Scientific Review Committee (SRC) (Required for studies involving cancer)

Institutional Biosafety Committee (IBC) (Required for studies involving the use of gene transfer and vaccines)

Investigational Device Review Committee (IDRC) Review by the IDRC is required for all protocols involving the use of investigational or marketed devices

Billing Grid (Required for all studies involving billing for hospital/clinic services)

Coverage Analysis (Departments requiring this analysis have been specified by the Organization)

Conflict of Interest (COI) Management Plan (Required for all studies with declared COI by study personnel)

Sponsored Programs Administration (SPA)/UNeHealth grants and contracts

Pathology approval for collection of tissue samples required for this study

Radiation Committee Approval

Other Review

♦ **None of the above organizational requirements apply to this study**

SECTION IV

COVID-19

Human Subjects Research Safety Plan

For studies involving face-to-face encounters, the research team under the responsibility of the principal investigator will agree to comply with the following safety measures:

1. Masking of the researcher(s) during a face-to-face encounter
2. Cleansing of any surface and/or equipment utilized before and after a subject encounter
3. The Biosafety Officer ([contact]) will be notified if obtaining saliva, nasal, sputum or stools samples to ensure safe collection, handling, and processing plan is in place
4. Suggest addressing the current health of the subject before commencing face-to-face research via questions below:
 - Have you or anyone in your household tested positive or had a fever, chills, cough, shortness of breath, diarrhea, nausea, vomiting, recent loss of taste or smell, tiredness or fatigue, or muscle aches? If yes, the monitor will not be allowed on campus.
 - Have you recently traveled to an area with a widespread outbreak or had close contact with a person known to have COVID-19, MERS-CoV or Ebola?
 - Have you traveled outside of the country within the past month? If so, where did you travel and when did you return?
 - Have you had a recent SARS-CoV-2 antibody test or nasal swab and if so when and what were the results?

♦ I acknowledge this requirement.
